#### Table 6. Short-form overview of the two treatments

#### Criteria for discontinuing or modifying allocated interventions $_{\{11b\}}$

If scheduling or the availability of equipment (surface, chair) hinders the participant from following the exercise dosage, the treating physiotherapist will, together with the participant, try to amend the programme to better suit the preferences and context of the participant while still aiming for the correct dose and form in accordance with the original approach to the fullest extent possible.

#### Intervention adherence {11c}

Making exercises enjoyable, social, and convenient has been identified as the most likely barriers to exercise adherence in adolescents with musculoskeletal pain. In line with this, the exercises prescribed in both groups are designed to be performed with only little if any exercise-equipment and are time-efficient (1-20 minutes per day/every other day). We also encourage the participants to attend their regular sports team practices and perform the exercises in that environment, rather than potentially skipping practice altogether, and thereby gaining a social aspect of performing the exercises. In both groups, the intervention personnel will remind participants to adhere to their respective interventions at visits at months 0, 1, 2, and 3. Reminders will firstly focus on the importance of adhering to dose and form of exercises and to the advice on loading by their own autonomy. Secondly, the personnel will engage participants in potential context-based barriers to adherence and foster realistic expectations. Through weekly monitoring, participants are asked about their adherence to exercise and other group-specific modalities the past week (table 7-9 and figures 8-10). Also, we ask if they have currently returned to sports participation. In addition to weekly reports on adherence, participants will be asked at visits at months 1 and 3 about their current exercise dose and to demonstrate the exercises, which will then be rated by the observing therapist on a standardized form (table 7). To ensure honest answers regarding adherence, data from weekly monitoring will be unavailable to the treating physiotherapist, and the participant will be informed of this blinding at enrollment. Capturing detailed adherence of participants will allow post-hoc interpretation of the study results beyond the intention-to-treat approach.

Table 7. Items for exercise evaluation forms as reported by the treating physiotherapist				
	Balance/alignment exercises	Stretching	Hip abduction	Knee exercise
	Comparator group		Experimental group	
Sufficient focus on knee alignment	х			
Sufficient focus on hip alignment	х			
Sufficient attention to progression	х		Х	х
Sufficient range of motion	Х	х	х	х
Sufficient load (RM)			х	х
Accurate tempo and time under tension	Х	х	х	х
Sufficient form to target to intended muscles or qualities	Х	х	х	х
Intended pain level (<3 NPRS)			х	х

#### **Compliance criteria**

Adherence will be determined in 3 different epochs, which will vary between groups, as the experimental intervention is divided into two phases. In the experimental group, two epochs will be set from month 0-1 (phase 1) and month 1-5 (phase 2 and the self-management period). The comparator group will only have 1 epoch lasting the whole core study period (month 0-5). We have outlined criteria for weekly adherence criteria below (table 7-9 and figures 8-10). For phase 1 in the intervention group, 3 out of 4 weeks of full adherence is considered as compliant, and for phase 2 (week 4-13), 7 out of 9 weeks of full adherence is considered compliant. For the whole treatment period in the comparator group (week 0-13), 10 out of 13 weeks with full adherence is considered compliant, this mirroring the total count in the same period in the intervention group. For the self-management period (months 3-5), in both groups, the criteria for exercises are the same as during treatment, but the dose is self-chosen. For participants in either group, the compliance criteria must be achived in every epoch, the to be catogrized as compliant over the entire study periode (month 0-5)

Epoch	Modality	Criteria for epoch	Measurement
Month 0-1 (phase 1)	Break from sports and	≤15 min of VPA and ≤30	Sensor-based
	MVPA	min of MPA every day	
	Daily isometric knee-extensor	4≥ full sessions per week	Weekly text: "How many sessions did you complete of
	exercise		your knee exercise this past week?"
Month 1-3 (phase 2):	Gradual exposure to sport with	Non-negative 4 week	Sensor-based
	limitation of pain flares	moving average of MVPA	
		minutes (calculated from	
		week 8)	
	Weightbearing knee-extensor	2≥ full sessions per week	Weekly text: "How many sessions did you complete of
	exercise every other day		your knee exercise this past week?"
Month 0-3 (phase 1 & 2)	Hip-abductor exercise	2≥ full sessions per week	Weekly text: "How many sessions did you complete of
	every other day		your hip exercise this past week?"
Month 3-5 (Self-	Self-chosen dose of knee-	2≥ sessions per week	Weekly text: "How many sessions did you complete of
management phase)	extensor exercise		your knee exercise this past week?"
	Self-chosen dose of any hip-	2≥ sessions per week	Weekly text: "How many sessions did you complete of
	abductor exercise		your hip exercise this past week?"
	No dramatic short-term	≤100% change in 4 week	Sensor-based
	changes in sports and	moving average of MVPA	
	physical activity	minutes	

Table 8. Adherence	criteria for the	e intervention group
--------------------	------------------	----------------------

Table 9. Adherence criteria for the comparator group					
Epoch	Modality	Criteria	Measurement		
Month 0-5	Balance and alignment exercises every other day	2≥ full sessions per week	Weekly text: "How many sessions did you complete of your balance exercise this past week?"		
	Daily quadriceps stretching	4≥ full sessions per week	Weekly text: "How many sessions did you complete of your stretching exercise this past week?"		
	Cryotherapy, sports taping, or patella strap	Utilized >1 times per week	Asked during visits: "How many times weekly have you used icepacks, taping, or straps?"		

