#### 3) Use of a patella strap

Each participant is given and instructed in the use of a patella strap according to manufacturer instructions (item 992, Mueller Sports Medicine Inc., Prairie du Sac, USA). The participants are instructed to use the patella strap if they are experiencing pain and find relief in using of the patella strap. They are also instructed to use the patella strap during sport or physical activity if they experience it as beneficial.

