#### 4) Advice on other modalities

**Cryotherapy**: "Utilize after participating in sports or physical activity if you experience pain or swelling. Apply the icepack for 15-20 minutes, and repeat if necessary". In addition, instructions on exactly what to use as an ice-pack and how to wrap it, and how to apply it safely.

**Taping:** "Specific taping of the knee can be useful for some if you have access to it. Maybe you have previous experience with applying sports-tape for your knee pain either on your own/with your parents, or by a coach, teammate, or health professional at your club."

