# Appendix 4: Weekly monitoring via text-messages (Danish)

[figure not shown]
[figure not shown]

Figure 10. Flow of text-based monitoring in the usual care group from week 0 to 22	
Question 1	
Hvor mange timer vil du sige, at du i alt har deltaget i sport, i sidste uge (uge <previous_week_number>)? Det gælder også sport i forbindelse med idrætsundervisning, i skolegården, eller i fritiden. 0 = Jeg har ikke dyrket sport overhovedet 1 = 0-30 minutter over hele ugen 2 = 30-60 minutter over hele ugen 3 = 1-2 timer over hele ugen 4 = 2-3 timer over hele ugen 5 = 3-5 timer over hele ugen 6 = Mere end 5 timer over hele ugen</previous_week_number>	
Reply	
Question 2	
Hvor mange gange i sidste uge har du oplevet, at dine knæsmerter har været på 4 eller mere, på 0-10 smerte-skalaen (0=ingen smerter, 10=værst tænkelige smerter)? Svar med et helt tal for antal gange.	
Reply	
Question 3	
Hvor mange dage i sidste uge har du lavet din udspændings- øvelse? Svar med et helt tal (0 til 7) for antal dage.	
Reply	
Question 4 Hvor mange dage i sidste uge, har du lavet din balance-øvelse?	
Svar med et helt tal (0 til 7) for antal dage.	
Reply	
Question 5	
Hvilket niveau er du nået til i balance-øvelsen?         1 = Et-bens stand i 30 sekunder         2 = Side-løft         3 = Halv-måner         4 = Side-drej         5 = Supermand         6 = Udfald	
Reply	
End of survey	
Tak for dine svar. Husk at åbne din SENS-app rimelig tit, f.eks. mens du laver dine øvelser. Du skal også huske at skrive ned hvornår du evt. har skiftet plaster.	

[figure not shown]

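### Two per-protocol compliance criteria are defective: the phase-2 MVPA row cannot be failed by any observed data, and as-needed aids are a usual-care requirement with no exemption

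*Combined protocol and SAP*

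**What the plan says.** Methods for additional analyses (20b) plans a per-protocol analysis, based on the pre-specified compliance criteria, to test the robustness of the primary intention-to-treat result. Those criteria are in the section Compliance criteria and in Tables 8 and 9.

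- **Week counts.** The experimental arm needs 3 of 4 fully adherent weeks in phase 1 and 7 of 9 in phase 2 (weeks 4 to 13). For usual care, "10 out of 13 weeks with full adherence is considered compliant". Every epoch must be passed for a participant to count as compliant over months 0 to 5. The term full adherence is not defined.
- **Table 8, phase 2.** The sensor row for gradual exposure to sport requires a non-negative 4-week moving average of MVPA minutes, calculated from week 8. The self-management row of the same table is worded differently, as a limit on the change in that average.
- **Table 9, aids row.** Cryotherapy, taping or strap must be "Utilized >1 times per week" over months 0 to 5. It is measured by a question at visits: "How many times weekly have you used icepacks, taping, or straps".
- **Advice on the aids.** Usual-care participants are "instructed to use the patella strap if they are experiencing pain and find relief", and may "use the patella strap during sport or physical activity if they experience it as beneficial". Ice: "Utilize after participating in sports or physical activity if you experience pain or swelling". Tape: "Specific taping of the knee can be useful for some if you have access to it".
- **Weekly data.** The section Intervention adherence says the weekly monitoring covers exercise and other group-specific modalities. The usual-care text flow in Appendix 4 ("Figure 10. Flow of text-based monitoring in the usual care group from week 0 to 22") has five questions: sport hours, pain episodes, stretching days, balance-exercise days and balance level. None concerns ice, tape or strap.

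**The concern.** A compliance rule should separate participants who followed their allocated treatment from those who did not. The MVPA row separates nobody. It is the only sensor check on gradual exposure in phase 2, yet someone who never resumes activity passes it.

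The aids row can separate on the wrong thing. A usual-care participant can follow the advice exactly and still fail because the knee stopped hurting, because the strap gave no benefit or because no tape was at hand. Membership of the compliant set would then depend partly on a post-randomisation symptom state related to the outcome.

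What is at stake is the per-protocol check alone. As written, an analyst has to invent a meaning for one row and a scoring rule for the other, after recruitment has closed at 130 of 130 (Trial status).

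**Working it through.** **Inputs.** Thresholds 3 of 4, 7 of 9 and 10 of 13 (Compliance criteria). MVPA row computed from week 8 (Table 8). Aids row of more than one use per week (Table 9). Adherence visits at months 1 and 3 (Table 11), taken as weeks 4 and 13. The tables' session criteria are read as minimums.

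**The plan's own figure.** The usual-care threshold is said to mirror the experimental total over the same period: 3 + 7 = 10 adherent weeks out of 4 + 9 = 13. This reproduces 10 of 13.

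**MVPA row, as written.** For weekly minutes x ≥ 0, MA(t) = (x_t + x_{t-1} + x_{t-2} + x_{t-3})/4 ≥ 0 always. A series collapsing from 400 to 0 minutes over nine weeks (400, 350, 300, 200, 100, 50, 20, 0, 0) gives averages 312.5, 237.5, 162.5, 92.5, 42.5 and 17.5: no failures. Phase 2 covers weeks 5 to 13, and the row has a value only in weeks 8 to 13. That is 6 of 9 weeks, all passing. The plan does not say how weeks 5 to 7 are scored on this row.

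**MVPA row, if a change was meant.** MA(t) − MA(t−1) = (x_t − x_{t−4})/4. With both windows inside phase 2, changes exist for weeks 9 to 13, so there are 5. The collapsing series now fails 5 of 5. The 7-of-9 rule allows 9 − 7 = 2 misses, so three decreases leave 6 (fail) and two leave 7 (pass), if all other rows are met and weeks without a value are judged on those rows. Now assume stable activity with independent, identically distributed, continuous weekly values. Reversing time turns every increase into a decrease, so the number of decreases D has the same distribution as 5 − D, and P(D ≥ 3) = 0.5. A strict no-decrease rule would fail about half of participants whose activity is stable.

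**Aids row, if full adherence means every row.** Usual care may miss 13 − 10 = 3 weeks. With perfect exercise adherence:

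| Weeks without enough aid use | Adherent weeks | Compliant |
|---|---|---|
| 3 | 13 − 3 = 10 | yes |
| 4 | 13 − 4 = 9 | no |

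The documents do not say how often such weeks occur. As an illustration only, if weeks are independent and the aids are used often enough in a week with probability 0.5, 0.7, 0.8 or 0.9, the chance of reaching 10 of 13 is 0.046, 0.421, 0.747 or 0.966 (binomial tail).

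**Linking visit answers to weeks.** No rule is given. If each visit answer were applied to all weeks since the previous adherence visit (an assumption), one low answer would leave 13 − 4 = 9 weeks (month 1) or 13 − 9 = 4 (month 3), both below 10. If the row sits outside the weekly count, the maximum is 13, but then nothing says how the row enters.

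**Months 3 to 5.** Weeks 14 to 22 are 22 − 13 = 9 weeks. Exercise criteria are given for them but no week count in either arm, although compliance is required over months 0 to 5.

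**The case against.** The strongest reply is that the aids problem is not proven. Table 8 heads its column as criteria for the epoch, Table 9 gives one epoch of months 0 to 5, and the aids row is asked at visits while both exercise rows use the weekly text. On an epoch-level reading, the 13 − 4 = 9 arithmetic does not apply. That stands as a limit. A reader might infer that usual-care participants are certainly misclassified, but the documents support this only if full adherence means every row. That is still the natural reading, because Compliance criteria introduces the tables as weekly criteria, and no other rule is offered.

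Symptoms are also not the only driver. Any one of three aids counts, and the strap may be used in sport for perceived benefit without current pain. So compliance depends partly, not wholly, on symptom state.

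The MVPA row may be a wording slip for a change or trend. That is likely, given the neighbouring row, but the written criterion still checks nothing.

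Epochs and criteria differ between arms by design, and the experimental arm has a demanding phase-1 sensor row (at most 15 minutes of vigorous and 30 of moderate activity every day) with no usual-care counterpart. It would therefore be wrong to infer that experimental compliance is easier overall.

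Finally, the standard analysis is intention-to-treat. That limits the severity of the point but does not remove it.

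**Conclusion.** Both criteria need repair before the per-protocol analysis is run. The MVPA defect holds however full adherence is read: 6 of 6 computable weeks pass for any observed data. The aids defect holds on the every-row reading, where four weeks without sufficient aid use are enough to make an otherwise fully adherent participant non-compliant. Separately, three places conflict on how aid use is recorded: Intervention adherence implies weekly, Table 9 says at visits, and the Appendix 4 text flow has no aids item.

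A reader might infer that the per-protocol result will favour the experimental arm because improved usual-care participants drop out of the compliant set. The documents do not support that. They give no frequency of aid use, no relation of aid use to the outcome and no expected exclusions by arm, so direction and size are unknown. Nor is the primary analysis or the sample size touched. Severity is minor to moderate.

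**What to change.** Issue a dated clarification before unblinding, written by people blinded to outcomes by arm. This matters because the study director curates the data and is unblinded to allocation. Existing data suffice.

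1. Define full adherence, for the per-protocol analysis, by the exercise items collected weekly plus the computable sensor criteria in the experimental arm. Take the aids out of the count and report their use descriptively. Reconcile the three passages on how aid use is recorded.
2. Leave the phase-2 MVPA row out of the main per-protocol definition. Add it in a sensitivity run, restated as a change or trend in the moving average, with a pre-stated tolerance and first computable week (8 or 9). Do not use a strict no-decrease rule as the main definition: it fails about half of stable participants under the assumption above, and it conflicts with the section Loading from sport and physical activity, which lets load be regressed for pain. Those passages must be reconciled.
3. State the week count for months 3 to 5, or limit per-protocol compliance to weeks 0 to 13.
4. Report exclusions per criterion and arm.

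The cost is wording in two tables and the section above them, one extra analysis run and a dated amendment. The per-protocol sets will change in size, and usual-care participants who needed the aids but did not use them will count as compliant. No treatment advice changes.

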# Criteria for discontinuing or modifying allocated interventions {11b}

If scheduling or the availability of equipment hinders the participant from following the exercise dosage, the treating physiotherapist will, together with the participant, try to amend the programme to better suit the preferences and context of the participant while still aiming for the correct dose and form in accordance with the original approach to the fullest extent possible.

#### Concomitant care during the trial {11d,30}

Participants will be encouraged only to receive treatment as outlined in their allocated group for the duration of the treatment (first 3 months) and the self-management period (month 3-5). Concomitant treatment will not be course for exclusion, but will be recorded at visits months 1, 3, and 5. We do not expect a high occurrence of concomitant treatment, but if this should occur, we will explore potential posthoc moderation or subgroup analysis to better understand this aspect and its implications on the results of the trial. Participants will be instructed to not take any pain medication on the same day of testing to ensure that this does not affect any measurements. No post-trial treatment is planned.

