Osgood-Schlatter affects up to 1 in 5 physically active adolescents and is the most common growth-related injury. The condition affects the knee, specifically the proximal tibial apophysis (the weakest part of the muscle-tendon-bone complex). Osgood-Schlatter can lead to long-term pain, swelling, and most notably, potential discontinuation of sports and physical activity, with potential sequela into adulthood. Osgood-Schlatter might also predispose to maladaptation in the maturing bone, inhibition of muscle activation, or more serious traumatic knee injuries, such as tendon-avulsion and ligament tear. Increased loading from sports participation seems to be a trigger as adolescents who practice more have a higher rate of Osgood-Schlatter. Data have also shown that adults who suffered sports-related injuries during youth are prone to musculoskeletal problems and poor health and having suffered knee pain before adulthood increase the risk of chronic pain later in life. In addition, investigations into longstanding knee pain in adolescence have shown that suffering from knee pain is related to lower quality of life, general health, and sports participation.

Research into Osgood-Schlatter and other lower limb apophysitis is only just emerging despite its first documentation in 1903. Only trials on injection therapy exists, and the recommended types of modalities for conservative management of Osgood-Schlatter is abundant and conflicting in the literature, reflecting the lack of evidence in this area for first-line conservative treatments.

The notion that adolescent knee pain is self-limiting with a favorable prognosis is widespread but recent data suggest this is not the case, as even when treated, it can be long-lasting. This presumption might partly explain the state of the current management of Osgood-Schlatter, being characterized by a wealth of advice, from total cessation of sport, participation under the pain-limit, play-through-pain, wait-and-see, and cast-immobilization; to passive therapies such as shockwave therapy, ultrasound therapy, laser therapy, injections, surgery, vitamin-supplements, cryotherapy, dry-needling, massage, stretches, and manual manipulations.

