## Sample size considerations {14}

The properties of the primary outcome measure KOOS-child and the "Sport/rec" subscale have been well investigated, with a validation study including adolescent participants with Osgood-Schlatter amongst other overuse- and acute knee disorders. A small cohort of patients in our clinic (n=16) who 1) were eligible for inclusion in the trial at baseline, 2) received the intervention in question and 3) attended follow-up, reported their global rating of improvement on a 7 point Likert scale ranging from 'much worse (7)' to 'much better (1)'. Patients who reported 'much better (1)' or 'better (2)' had a mean improvement on KOOS-child

'Sport/play' subscale of 12.7±16 points, whereas patients reporting less improvement ('little' improvement or 'no change') only had a 3.57 point increase. In absence of more robust specific data in terms of severity, intervention, and length of follow-up, we will utilize this 9 point difference as a threshold for determining superiority. We consider this to be a meaningful change and a relevant between-group difference, and is within the recommended range of 8-10 points (heartbeat-med.com/resources/knee-injury-and- osteoarthritis-outcome-score-koos). This change also exceeds the smallest detectable group-level change (2.66 points) and the standard error of measurement (8.02 points).

In order to detect such a change with a standard deviation of 16 points an  $\alpha$  level (type I/false positive error rate) of 5% and power ( $\beta$ -1, or probability of avoiding type II/false negative error rate) of 90%, 55 (54.8) participants per group would be needed based on an independent one-sided t-test (R 4.0.2, Foundation for Statistical Computing, Vienna, Austria; RStudio 1.0.153, power.t.test package). To account for a potential 15% dropout rate a total of 130 participants will be included.

This will correspond to a 0.56 Cohens d 'medium' effect size at 90% power (figure 3). The smallest effect size reliably detectable will thus be >0.482 (Cohens d 'small' effect size) at  $\geq$ 80% power (Jamovi 1.2.25, jpower module), surpassing the trivial (<0.2) and small (>0.2) effect size thresholds. We also consider this sample size to be operationally feasible within the given timeframe and with the resources available to our group.

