# Data collection and management

## Plans for assessment and collection of outcomes {18a}

Depending on the time point, participants will answer between 85 (baseline) and 38 questions (month 1) in their surveys. In table 11 we have described the schedule of data collection of all outcomes. All outcome data, both clinically obtained by an outcome assessor or patient-reported directly from the participants, will be entered into REDCap. Weekly monitoring will be performed using text-based service (SMS-track®, Esbjerg, Denmark) similarly starting the following Monday after the baseline visit and the following 22 weeks, totaling 23 weekly monitoring questionnaires containing 4-6 questions.

Study phase	Pre-allocation	Baseline	Intervention period				Primary endpoint	Clinical follow-up	Long-term follow-up d
Timepoint		Mo 0	Weekly	Mo 1	Mo 2	Mo 3	Mo 5	Mo 8	Mo 10, 12, 24 48
Enrollment procedures					 	 		•	•
Clinical visit		Х		Х		Х	Х	Х	
At home	Х		Х		Х				Х
Phone screening	Х								
Written information	Х	Х							
Verbal information	X	Х							
Written consent		Х							
Allocation		Х							
Clinical assessments	1								
Clinical examination		Х					Х		
Peak Height Velocity		Х				Х	Х	Х	
Adverse events		Х		Х	Х	Х	Х	Х	
Previous & concomitant treatments		Х		Х	х	Х	Х	Х	
Clinical tests							-		
Pressure-Pain threshold		Х		Х		Х	Х	Х	
Knee extension strength		Х		Х		Х	Х	Х	
Countermovement jump		Х		Х		Х	Х	Х	
Modified Thomas test		Х		Х		Х	Х	Х	
Anterior knee pain provocation test		Х		Х		Х	Х	Х	
Objective longitudinal measures	-ii								
Physical activity (sensors)		•							
Imaging	1								
Ultrasound scanning		Х				Х	Х	Х	
Patient-reported questionnaires									
KOOS-child 4 subscales		Х		Х	х	Х	Х	х	Х
Acceptable Symptom State (PASS)		Х		Х	х	Х	Х	Х	Х
Global rating of change				Х	х	Х	Х	Х	Х
Sport & Physical activity		Х	Х	Х	х	Х	Х	Х	Х
Pain history		Х	Х	Х	х	Х	Х	Х	Х
Self-rated health (EQ-5D-Y)		Х				х	Х	Х	Х
Kinesiophobia (Tampa)		Х				Х	Х		
Therapeutic Alliance (WIA)						х			
Miscellaneous health a		Х							
Pubertal stage (Tanner)		Х				х	Х		
Adherence to treatments			Х	х		х	Х	Х	
Intervention									
Experimental or usual care treatment		—							
Complete self-management		•				.			

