## Methods for additional analyses (e.g. subgroup analyses) (20b)

Besides the sensitivity analyses otherwise specified (covariate adjusted, mixed-effects, moderation, mediation), we will perform per-protocol analyses to test the robustness of the primary intention-to-treat analysis, by examining the effect of adherence according to the pre-specified compliance criteria.

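### Concomitant treatment begins after randomisation, so the planned moderation or subgroup analysis by its use can misstate the treatment effect in users and non-users, in either direction

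*Combined protocol and SAP*

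**What the plan says.** The section on concomitant care asks participants to keep to their allocated treatment through month 5. Other treatment does not lead to exclusion and is recorded at months 1, 3 and 5. High use is not expected. Should it occur, the one stated response is: "we will explore potential posthoc moderation or subgroup analysis to better understand this aspect and its implications on the results of the trial". The section gives no method, assumption or caution for that analysis.

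Three other places bear on it:

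- **Eligibility.** Patients unwilling to stop current Osgood-Schlatter treatment are not included. Treatment recorded during the trial is therefore, in principle, begun or resumed after allocation.
- **Statistical methods.** Analysis by allocation is the standard strategy, justified partly by the need to keep the balance that randomisation creates.
- **Effect moderation and mediation.** Variables measured after randomisation and thought to be influenced by allocated treatment are classed as mediators. The assumptions section adds that they are not randomised and that their relation to outcome can be confounded.

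The study schedule (Table 11) has a row "Previous & concomitant treatments", marked at baseline and months 1, 2, 3, 5 and 8. The additional analyses include a per-protocol analysis, "by examining the effect of adherence according to the pre-specified compliance criteria". Those criteria (Tables 8 and 9) cover only the participant's own-arm exercises, activity and aids.

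**The concern.** A moderator or subgroup variable should be fixed before randomisation. Then each stratum is itself a randomised comparison. Use of other care is not fixed in that way: a participant who is doing badly is more likely to look for it, and if one arm does better, fewer of its members will. Non-users in usual care are then a more strongly selected group of good responders than non-users in the experimental arm, and users in the experimental arm are a more strongly selected group of poor responders. Within each stratum the arms differ for reasons other than treatment.

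The background section shows that plenty of other care is available: "shockwave therapy, ultrasound therapy, laser therapy, injections, surgery, vitamin-supplements, cryotherapy, dry-needling, massage, stretches, and manual manipulations". The stated purpose of the analysis is to judge what concomitant care implies for the trial's results. A biased answer could lead the report to say that the effect shrinks, or grows, once other care is taken into account, when nothing of the kind has happened. The plan's own reasoning on intention to treat and on mediators warns against this, but it is not applied here.

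**Working it through.** **Inputs from the documents (sample size section).** Difference 9 points: "we will utilize this 9 point difference as a threshold for determining superiority". SD 16: "In order to detect such a change with a standard deviation of 16 points". One-sided test at 5% with 90% power: "participants per group would be needed based on an independent one-sided t-test".

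**The plan's own figure.** A one-sided t-test with these inputs needs 54.82 per group, rounded to 55, which matches the plan. Allowing for 15% dropout, 110 / 0.85 = 129.4, or 130 in total, also as stated. Nothing below changes the sample size.

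**Assumptions, not in the documents.** Overall use is 10-50%. A participant uses other care when early progress falls below a cut-off that is the same in both arms. Treatment shifts early progress by 9/16 = 0.5625 SD. Within each arm, early progress correlates r with the month-5 change. The other care has no effect of its own. The true effect is 9 points in everyone.

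**Formula.** Let z be the standardised cut-off in an arm, φ and Φ the normal density and distribution function, λ(z) = φ(z)/Φ(z) and μ(z) = φ(z)/(1 − Φ(z)). With A the experimental arm and C usual care:

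- users: 9 − 16·r·[λ(z_A) − λ(z_C)]
- non-users: 9 + 16·r·[μ(z_A) − μ(z_C)]

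**Worked case: 20% overall use, r = 0.7.** The cut-offs are z_A = −1.156 and z_C = −0.594, giving use of 12.4% and 27.6%.

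- users: 9 − 16 × 0.7 × (1.652 − 1.211) = 9 − 4.9 = 4.1
- non-users: 9 + 16 × 0.7 × (0.233 − 0.462) = 9 − 2.6 = 6.4

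**Apparent effect, users / non-users (true value 9.0 / 9.0):**

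| Overall use | Use in A / C | r = 0.5 | r = 0.7 |
|---|---|---|---|
| 10% | 5% / 15% | 5.2 / 7.8 | 3.7 / 7.3 |
| 20% | 12% / 28% | 5.5 / 7.2 | 4.1 / 6.4 |
| 30% | 20% / 40% | 5.7 / 6.8 | 4.3 / 5.9 |
| 50% | 39% / 61% | 6.1 / 6.1 | 5.0 / 5.0 |

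A simulation with 2 million per arm agrees to within 0.1 point, and its as-randomised difference stays at 9.0. A spurious interaction also appears: about −2.4 points at r = 0.7 and 20% use.

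**Where the bias vanishes or reverses.**

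- r = 0 (use unrelated to outcome): 9.0 / 9.0.
- Use depends on prognosis only, with the same rate and selection in both arms (r = 0.7, 20%): 9.0 / 9.0.
- Use of 20% in the experimental arm and 10% in usual care, r = 0.5: users 9 − 8 × (1.400 − 1.755) = 11.8; non-users 9 + 8 × (0.350 − 0.195) = 10.2. Both are inflated.

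**If the other care helps.** With an assumed gain of 4 points from it, the as-randomised difference is 8.2-8.6 at 10-30% use. That is the effect of being offered each arm with other care as it occurs.

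**Precision.** At 20% use and 55 analysed per arm, about 55 × 0.124 = 7 experimental and 55 × 0.276 = 15 usual-care participants are users. The standard error is about 16 × √(1/7 + 1/15) = 7.3 points.

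**The case against.** The strongest reply is that nothing planned rests on this analysis. It is conditional on unexpectedly frequent use, labelled post hoc, worded as exploration, and absent from the list of additional analyses. The main conclusion is to be framed on the between-group difference at the primary endpoint, analysed by allocation. All of that stands. A reader might infer that the primary result is compromised; the documents do not support this, since data are collected regardless of adherence and all participants are analysed as randomised.

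The reply continues that size and direction are assumed. That also stands. A reader might infer that the effect must look too small; that needs use that is driven by poor progress and commoner in usual care. Participants are blinded to the content of the other arm, so differential seeking of care is possible but not established. At 10% use the non-user estimate falls only to 7.3-7.8, and the user stratum is too imprecise to carry a firm claim.

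What does not stand is that the exploratory label makes the analysis harmless. It would be run only when use is high, which is when the larger, non-user stratum is most distorted. An analysis whose bias has no known sign cannot serve the explanatory purpose given for it.

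A reader might also infer that the per-protocol criteria should be tightened, because someone who receives outside treatment still counts as compliant. The observation about Tables 8 and 9 is correct, but requiring no other treatment would select the same non-user subset in each arm and carry the bias into an analysis that is firmly planned.

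**Conclusion.** The point holds as one of interpretation. The only stated response to frequent concomitant treatment conditions on a variable that allocation can affect, and the resulting stratum effects can be wrong in either direction. With 20-30% overall use, driven by poor progress and commoner in usual care, and a correlation of 0.5-0.7, a true 9-point effect appears as about 4-6 points in users and 6-7 in non-users. These figures illustrate and do not predict, because the documents give neither rates of use nor the correlation. The bias is smaller at low use, nil if use is unrelated to outcome or is the same in rate and selection in both arms, and reversed if the experimental arm uses more. The intention-to-treat estimate and the sample size are untouched.

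**What to change.** In the section on concomitant care, replace the moderation or subgroup analysis by concomitant treatment with:

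1. an explicit statement that the as-randomised comparison uses all data regardless of concomitant treatment (the plan already implies this; one sentence suffices);
2. a description by arm of the type, timing and proportion of concomitant treatment, as far as the forms record them;
3. a statement that moderators are limited to baseline variables. Table 12 labels its moderators as week 0 except fear of movement, labelled week 13, which should be checked at the same time.

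**Optional.** If the forms record when such treatment began, add one sensitivity analysis in the full randomised set that imputes month-5 KOOS-child Sport/play after other active treatment. Label it as a hypothetical estimand under missing at random. Its price is an untestable assumption and a wider interval. It is a choice of estimand that the plan does not require, and the documents do not show whether start dates are collected.

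Do not add absence of concomitant treatment to the per-protocol definition.

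Reconcile the recording months in the text (1, 3 and 5) with Table 11, which also marks baseline and months 2 and 8.

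The core change is SAP wording and one descriptive table. The sample size and the primary analysis stay as they are.
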